A referral for psychiatric evaluation is required for AE/serious adverse event (SAE) of suicidal ideation/suicidal attempt or significant increase in the suicidality scale from baseline (e.g. 2 point increase or higher) or C-SSRS (who answer "Yes" to questions 3, 4, and 5 in the scale suicidal ideation section) or PBA-s suicidality score 3 and above. All patients with PBA-s suicidal ideation item score  $\geq 3$  (i.e. 3, 4) will be discontinued from treatment with IMP. Patients who are discontinued from IMP may continue their participation in the study and perform the scheduled visits and assessments, while off IMP. They will continue to be closely monitored by the investigator (or qualified designee) and will be referred for psychiatric evaluation per the investigator's (or qualified designee's) medical judgment.

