##### **Suicidal Ideation or Suicidal Attempt**

AEs of suicidal ideation or attempt should be reported to the Sponsor within 24 hours of learning of the event (expedited reporting, regardless of seriousness). The corresponding dedicated eCRF should be completed, but the events should not be marked as serious unless deemed serious by the investigator (or qualified designee). The words "protocol defined AE" should be added after the AE term. Once the AE of suicidal ideation or attempt is received, the patient should be discontinued from the study and from IMP, and referred to a psychiatrist for evaluation and monitoring (see Section [7.7.2](#)).

Standard emergency medical procedures should be followed for any medical and safety concern when immediate intervention is needed (refer to protocol-specific Escalation Plan).

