### **7.7.1 Cessation of Treatment**

A patient will be classified as having ceased treatment when he or she discontinues IMP, prior to the completion of the prescribed course for any of the following reasons:

- AE
- Death
- Lost to follow up
- Patient withdrew consent
- Major protocol violation
- Pregnancy

- 
- Treatment is no longer appropriate
  - Termination of study

If hypokalemia is observed, dosing will be interrupted and should not be started again until normal electrolyte values are confirmed by re-draw and maintained for 7 days. Patients needing more than 14 days to reach stable potassium levels, without IMP, should be withdrawn from the IMP. The patient will be asked to continue in the study and follow the visit schedule as outlined in the protocol.

In instances where there is an increase in QT/QTcF of >500ms or 60ms over VTV, a second ECG should be repeated after 10 minutes rest to confirm the finding. Where confirmed, this should be reported and documented on the eCRF as an AE.

Patients with a QTcF interval of >500 ms, or with an increase in the average QTcF value >60 ms from the VTV, should be discontinued from the study. A follow-up ECG should be done in 4 weeks.

Patients should also be discontinued if:

- they experience a seizure or convulsions (regardless of the relationship to treatment);
- their body weight decreases to <50 kg (may be discontinued based on investigator (or qualified designee) or Sponsor discretion);
- and/or if creatinine clearance decreases to <60 mL/min (calculated using the Cockcroft-Gault equation). It is allowed to repeat the test once, if clinically appropriate.
- they experience an AE/SAE of suicide ideation or attempt; or
- they have a C-SSRS suicidal ideation score  $\geq 3$  (i.e. who answer "Yes" to questions 3, 4, and 5 in the scale suicidal ideation section); or
- they have a C-SSRS report of suicidal act; or
- they have an abbreviated PBA-s suicidal ideation item score  $\geq 3$  (i.e. 3, 4).

Patients who discontinue treatment with IMP due to safety or tolerability reasons may continue in the study off IMP and perform the scheduled visits and assessments.

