### **7.7.2 Withdrawal**

Patients have the right to discontinue IMP at any time and for any reason. The investigator (or qualified designee) also has the right to discontinue IMP if he/she feels that treatment is no longer appropriate, if in his/her opinion the patient's clinical condition is worsening or for an AE(s).

A complete evaluation, as detailed in the study protocol for the EOS Visit, should be carried out at the time of discontinuation. The patient will then be withdrawn from the study.

If the reason for premature discontinuation is an AE or an abnormal laboratory test result, the principal specific event or test must be reported on the appropriate section(s) of the eCRF.

All patients for whom an AE of suicidal behavior/ideation was reported at any time during the study should be discontinued from IMP and the need for an evaluation by a psychiatrist should be assessed. Discontinued patients should attend an ET visit remotely to return IMP, perform IMP accountability, and will be asked to complete all protocol required study procedures. AEs of suicidal behavior/ideation should be followed until resolution of the suicidal behavior/ideation.

All patients who are discontinued from the IMP due to active suicidal behavior/ideation should be referred to a psychiatrist and followed by the investigator (or qualified designee) until resolution of the suicidal behavior/ideation.

Patients who discontinue IMP due to safety or tolerability reasons may continue in the study off drug and perform the scheduled visits and assessments.

A patient will be considered to have withdrawn from a study in the following circumstances: death, lost to follow-up, if the patient has withdrawn informed consent, or the investigator (or qualified designee) feels that the treatment is no longer appropriate. If withdrawal is due to an SAE the procedure detailed in Section 7.5.3 should be followed.

Patients with a QTcF interval of >500 ms or if an increase in the average QTcF value is >60 ms from the VTV should be discontinued from the study. A follow-up ECG should be done in 4 weeks.

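### Psychiatric referral is mandatory in one place and discretionary in another for two groups: suicidality adverse events not classed as active, and patients scoring 3 or more on the PBA-s suicidal ideation item

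*Protocol*

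**What the plan says.** **Protocol 4.7.3.** The referral paragraph begins: "A referral for psychiatric evaluation is required for AE/serious adverse event (SAE) of suicidal ideation/suicidal attempt". The sentence lists further triggers, including a PBA-s suicidality score of 3 or above. The next sentence stops study drug for anyone scoring 3 or 4 on the PBA-s suicidal ideation item. The paragraph continues: "Patients who are discontinued from IMP may continue their participation in the study and perform the scheduled visits and assessments, while off IMP". It closes by saying that these patients remain under close monitoring and "will be referred for psychiatric evaluation per the investigator's (or qualified designee's) medical judgment".

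**Protocol 7.4.** After an AE of suicidal ideation or attempt, "the patient should be discontinued from the study and from IMP, and referred to a psychiatrist for evaluation and monitoring". The sentence has no judgment qualifier and ends with a pointer to 7.7.2.

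**Protocol 7.7.1.** Its reasons for discontinuation include that "they experience an AE/SAE of suicide ideation or attempt" and, as a separate item, a PBA-s suicidal ideation score of 3 or 4.

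**Protocol 7.7.2.** There are two rules in consecutive paragraphs. Patients with a suicidality AE reported at any time "should be discontinued from IMP and the need for an evaluation by a psychiatrist should be assessed". Then: "All patients who are discontinued from the IMP due to active suicidal behavior/ideation should be referred to a psychiatrist".

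**The concern.** These sections cover overlapping events but differ in how firmly they call for referral: required, directed, need to be assessed, or left to judgment. Two sites facing the same event could act differently, and each could cite the protocol. SAP section 5.8 summarises protocol violations as recorded on the case report form, so whether a missing referral is recorded would depend on which section the site or monitor had read.

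The protocol treats suicidal ideation and attempt as events of special interest, to be reported to the sponsor within 24 hours whether or not they are serious. Its background section puts suicide in Huntington's disease at 4 to 8 times the general-population rate. That figure describes the disease as a whole. Section 4.5 excludes patients with past suicidal ideation or attempt AEs or past suicidal behavior, so the figure should not be read as the risk in this cohort.

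**Working it through.** No arithmetic applies. The check sets each rule beside each type of event.

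| Event | 4.7.3, opening | 7.4 | 7.7.2 | 4.7.3, close |
|---|---|---|---|---|
| Suicidality AE, drug stopped for active behavior or ideation | required | directed | directed (second rule) | not its immediate subject |
| Suicidality AE not classed as active | required | directed | need assessed (first rule) | not its immediate subject |
| PBA-s suicidal ideation item 3 or 4, no AE recorded | required | silent | silent, unless the stop counts as being for active ideation | investigator judgment |

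**Row 1.** All three sections lead to referral. The first rule in 7.7.2 is weaker, but the second rule in the same section supplies the direction. There is no material conflict.

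**Row 2.** Sections 4.7.3 and 7.4 call for referral, while 7.7.2 asks only for an assessment of need. Section 7.4 itself sends the reader to 7.7.2, and so to the weaker wording. The term *active*, on which the second rule turns, is not defined there, and neither 4.7.3 nor 7.4 makes that distinction. Section 4.7.3 also lets the investigator manage patients with suicidality scores of 1 or 2, with psychiatric consultation as needed. A low-scoring patient whose ideation is recorded as an AE and not called active therefore meets both a mandatory and a discretionary rule.

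**Row 3.** The paragraph in 4.7.3 requires referral at this score, stops drug at this score, and then makes referral of the patients it has just stopped a matter of judgment. Mandatory and discretionary wording apply to the same patients in one paragraph.

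**Reach of the closing sentence.** Grammatically it refers to patients taken off study drug. The sentence that leads into it concerns the PBA-s item, so those patients are its immediate subject. Patients with a suicidality AE are also taken off drug under 7.4, 7.7.1 and 7.7.2, so the sentence could be stretched to cover them, but the paragraph does not say that it does.

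**The case against.** - **Section 7.7.2 may intend two tiers:** assess need for any suicidality AE, and refer when drug is stopped for active suicidality. This is a fair reading, and it is why row 1 is not in conflict. It does not settle row 2, because the other sections have no such tier and the dividing term is undefined.
- **The close of 4.7.3 may mean further referral during off-drug follow-up,** after the required referral has been made. The words allow this, and nothing in them withdraws the earlier requirement. If it is what was meant, row 3 is not a conflict, but the text does not say so.
- **Referring the patient satisfies every section, and none forbids it.** That is true, and a site that does not refer has departed from an explicit requirement in 4.7.3. But a site that assesses need under 7.7.2 and decides against referral has followed that section as written. The difference in strength remains.
- **Other safeguards do not depend on the referral wording.** These are stopping the drug, 24-hour reporting, follow-up of these AEs until resolution, more frequent calls when C-SSRS ideation exceeds 2, and a protocol-specific Escalation Plan. They limit the consequences. The Escalation Plan was not supplied and may address referral.
- **The version reviewed may never have governed patients.** SAP section 2.1 says the analysis plan rests on Amendment 04 and that Amendment 05, the virtualization amendment, was not put into effect. This stands. The Amendment 04 referral wording is not in the documents, so they do not show whether it has the same conflict.

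**Conclusion.** The conflict is real and narrow. It covers suicidality AEs not classed as active (4.7.3 and 7.4 against 7.7.2) and patients at 3 or 4 on the PBA-s suicidal ideation item (opening against close of 4.7.3, unless the close means later referral). In both groups the instruction ranges from always refer to refer at discretion. The number of patients affected cannot be given, because the documents contain no event counts. No endpoint, analysis set or estimate is affected.

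A reader might infer three stronger things that the documents do not support:
- That 7.7.2 leaves every referral to judgment. Its second rule directs referral when drug is stopped for active suicidality.
- That the closing sentence of 4.7.3 overrides the requirement for every discontinued patient. Its context is the PBA-s item.
- That patients went unreferred. Nothing supplied shows conduct under this version.

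The conclusion assumes that the PBA-s suicidality score in the opening sentence and the suicidal ideation item in the next are the same measure, and that an attempt counts as active behavior under 7.7.2. Whether the patient stays in the study after such an event is a separate question, not judged here.

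**What to change.** Replace the wording in 4.7.3, 7.4 and 7.7.2 with one statement that lists each trigger and says whether psychiatric referral is mandatory or discretionary for it, and have the other sections refer to that statement. It should say whether *active* is a separate tier and, if so, define it. It should also say whether the closing sentence of 4.7.3 concerns the initial referral or later referral during off-drug follow-up. The sponsor's clinicians must decide the rule; this review takes no position on it.

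The sponsor should also check whether the Amendment 04 text and the Escalation Plan contain the same difference.

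The cost is wording in three sections. Data collection and the analyses in the SAP do not change.

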 Medical history collected prior to study virtualization will remain in a separate database while updated medical history will be collected at VTV.

 Test connections are to be completed at home (and/or applicable location) by the vendor prior to the first remote visit to ensure remote video conferencing equipment functionality.

 Information on benzodiazepines and antidepressants will be collected as part of the concomitant medication inquiry.

 The mobile nurse will complete the collection of safety laboratory tests, measurement of ECGs, and vital signs at home (and/or applicable location).

 Vital signs measurements include HR, BP, and weight.

- 
-  ECGs will be performed every 6 months unless a safety signal is detected. If a safety signal is detected, the mobile nurse will measure ECGs every 3 months. An ECG safety signal is defined as a QTcF  $\geq 480$  ms and  $\leq 500$  ms ( $\geq 60$  ms increase from VTV).
-  Urine pregnancy tests are to be performed as applicable based on gender and menopausal status. Serum pregnancy tests must be used to confirm a positive urine pregnancy test result.
-  Safety laboratory tests include potassium, magnesium, calcium, and creatinine clearance.
-  Creatinine clearance will be calculated using the Cockcroft-Gault equation. Patients that de-escalate to half-doses of IMP will have creatinine clearance monitored more frequently than patients at the full dose, as determined by the investigator (or qualified designee).
-  UHDRS includes Motor Assessment, Cognitive Assessment (Stroop Interference, Verbal Fluency, and Symbol Digit Modalities Test), Behavioral Assessment, Functional Assessment, Independence Scale, Total Functional Capacity, and Summary sections. UHDRS Motor exam will be modified as portions will be considered "unable to rate" (such as rigidity, tandem walking, and retropulsion pull test tasks).
-  The C-SSRS "Since Last Visit" version will be utilized at all visits. If the patient scores  $>2$  on the C-SSRS for suicidal ideation, the safety TCs should be performed monthly or bi-monthly per investigator (or qualified designee) judgement.

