#### 4.5 Exclusion Criteria

- [Revision 1] Ongoing treatment with tetrabenazine or deutetrabenazine, seizure threshold lowering medications, or certain antipsychotics and antidepressants (see Protocol Section 5.7 and current Operations Manual for list of disallowed medications).
- [Revision 2] Newly instigated or changed treatment with neuroleptics/anti-psychotics.
- [Revision 3] Use of tricyclic antidepressants or class I & III antiarrhythmics at any time during the study period.
- [Revision 4] Any clinically significant, abnormal laboratory result, including clinically significant hepatic or renal impairment, or any ongoing AE that, in the opinion of the investigator (or qualified designee), affects the patient's suitability for the study or puts the patient at risk if he/she continues in the study.
- [Revision 5] A prolonged QTc interval at the RV1 (defined as a QTcF interval of >450 ms for both males and females using Fredericia's formula) or other clinically significant heart conditions as judged by the investigator (or qualified designee).
- [Revision 6] Severe intercurrent illness that, in the opinion of the investigator (or qualified designee), may put the patient at risk when continuing participation in the study.
- [Revision 7] Alcohol and/or drug abuse as defined by the Diagnostic and Statistical Manual - Fourth Edition - Text Revision criteria for substance abuse – this includes the illicit use of cannabis.
- Patients with AEs of suicidal ideation or attempt at any time in the past or as measured by a suicide ideation score of  $\geq 3$  on the Columbia-Suicide Severity Rating Scale (C-SSRS) (who answer "Yes" to questions 3, 4, and 5 in the scale suicidal ideation section), or a score of  $\geq 3$  on the Problem Behaviors Assessment – Short Form (PBA-s), or patients who answer "Yes" on any of the 5 C-SSRS Suicidal Behavior Items (actual attempt, interrupted attempt, aborted attempt, preparatory acts, or behavior), if an attempt or acts were performed at any time in the past, or patients who, in the opinion of the investigator (or qualified designee), present a risk of suicide.
- Patients with a known history of epilepsy or a history of febrile seizure(s) or seizure(s) of unknown cause.
- Females who are pregnant or lactating.

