#### **4.7.3 Problem Behaviors Assessment – Short Form**

Because of the prominence of psychiatric symptoms in HD, it is recommended that the PBA-s form be used in all HD studies with any need for behavioral assessment as a comprehensive screen for the most common psychiatric symptoms in HD (Craufurd et al 2001; Kingma et al 2008). The PBA-s is a brief semi-structured interview covering the most common behavioral and psychiatric manifestations of HD. The interview is not restricted to a single construct, but rather covers several broad symptom domains relevant to HD, comprising 11 items: low mood, suicidal ideation, anxiety, irritability, anger/aggressive behavior, loss of motivation, perseverative thinking or behavior, obsessive-compulsive behaviors, paranoid thinking, hallucinations, behavior suggestive of disorientation. Each symptom is rated for severity on a 5-point scale according to detailed scoring criteria, which roughly correspond to the following: 0 = "not at all"; 1 = trivial; 2 = mild; 3 = moderate (disrupting everyday activities) and 4 = severe or intolerable. Each symptom is also scored for frequency on a 5-point scale as follows: 0 = symptom absent; 1 = less than once weekly; 2 = at least once a week; 3 = most days (up to and including some part of everyday); and 4 = all day, every day. Severity and frequency scores are multiplied to produce an overall 'PBA score' for each symptom.

Only the abbreviated PBA-s (i.e. items of the PBA-s relevant to suicidality [depressed mood, suicidal ideation, anxiety, irritability, loss of motivation, obsessive-compulsive behaviors]) will be collected during the TCs and virtual visits when the UHDRS is not completed. If the patient has a positive score 1 and 2 on the suicidal ideation item or depressed mood item of the PBA-s, the patient will be monitored more closely and treated according to the investigator's (or qualified designee's) medical judgment. Patients with C-SSRS or PBA-s suicidality scores 1 and 2 may be handled by investigator (or qualified designee)/neurologist with a consultancy with psychiatrist(s) where necessary per investigator's (or qualified designee's) medical judgement.

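### The C-SSRS threshold of 3 or more is explained as a yes to questions 3, 4, and 5, which read literally needs all three; separately, the PBA-s exclusion names no item

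*Protocol*

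**What the plan says.** Three decisions in the Protocol use the C-SSRS suicidal ideation result with the same explanatory phrase.

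- **Exclusion (Synopsis 1.1 and Section 4.5):** a score of at least 3, followed by the list of questions 3, 4, and 5.
- **Stopping (Section 7.7.1):** a score of at least 3, equated by 'i.e.' with a yes "to questions 3, 4, and 5 in the scale suicidal ideation section".
- **Psychiatric referral (Section 4.7.3):** required for a yes to "questions 3, 4, and 5 in the scale suicidal ideation section) or PBA-s suicidality score 3 and above".

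Two further statements use a C-SSRS cut without the list.

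- **Lower tier (Section 4.7.3):** "Patients with C-SSRS or PBA-s suicidality scores 1 and 2 may be handled by investigator", with psychiatric consultation where needed.
- **Footnote 17 to Section 1.3:** for a score above 2 "on the C-SSRS for suicidal ideation, the safety TCs should be performed monthly or bi-monthly".

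The PBA-s clause in the exclusion criteria asks for a score of at least 3 on the instrument and then moves on: "Short Form (PBA-s), or patients who answer". It names no item and does not say which rating is meant. Sections 4.7.3 and 7.7.1 do name the suicidal ideation item, and both specify the values 3 and 4.

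**The concern.** The word 'and' in a list of screening questions ordinarily means that every one must be answered yes. Taken that way, the explanation contradicts the score beside it: a patient can reach a score of 3 without a yes to questions 4 and 5. These are operative safety thresholds that decide entry, continued dosing and referral, in a disease for which Section 2.1 reports suicide 4 to 8 times more often than in the general population. Two sites could act differently on the same answers.

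The PBA-s clause errs in the other direction. With no item named, a moderate score on irritability or anxiety would meet an exclusion intended for suicidality.

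**Working it through.** **1. Comparing the cuts.** The lower tier ends at 2, footnote 17 acts above 2, and the exclusion and stopping rules print at least 3. These four statements agree that the upper tier starts at 3. Only the question list, read as all three, disagrees.

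**2. Is the literal list narrower under any plausible scoring?** Section 4.7.2 gives neither the number of ideation questions nor the scoring. I assume five yes/no questions (the text numbers them up to 5) and try two scorings: the highest-numbered question answered yes, and the count of yes answers.

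| Answered yes | Highest item | Count | All of 3, 4, 5 | Any of 3, 4, 5 |
|---|---|---|---|---|
| 1, 2, 3 | 3 | 3 | no | yes |
| 1, 2, 3, 4 | 4 | 4 | no | yes |
| 1 to 5 | 5 | 5 | yes | yes |
| 3 only | 3 | 1 | no | yes |

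The first two rows reach a score of 3 under both scorings and fail the literal list. Over all 2^5 = 32 answer patterns:

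- All of 3, 4 and 5: 2^2 = 4 patterns.
- Any of 3, 4 or 5: 32 − 2^2 = 28 patterns, exactly those with a highest-item score of at least 3.
- Count of at least 3: 10 + 5 + 1 = 16 patterns.

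The 4 patterns lie inside both the 16 and the 28, so the literal list is strictly narrower either way. The wording 'any of' reproduces the cut exactly only under highest-item scoring. These are counts of answer patterns and say nothing about how many patients are affected.

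**3. What the other triggers catch.** Referral also follows an adverse event of ideation or attempt (Sections 4.7.3 and 7.4), a PBA-s suicidality score of 3 or above, and a "significant increase in the suicidality scale from baseline (e.g. 2 point increase or higher". The 2-point limb names no scale. If it means the C-SSRS under highest-item scoring, there are 3 × 3 = 9 moves from a score of 0–2 to a score of 3–5. Eight are increases of at least 2, and only the move from 2 to 3 is missed. If it means the PBA-s item, a C-SSRS change alone triggers nothing. Whether a yes on the C-SSRS becomes an adverse event depends partly on the investigator's view of clinical relevance (Section 7.2.1). Section 7.7.2 sends patients stopped for active ideation to a psychiatrist, but the score-based stop in 7.7.1 carries the same question list. At entry, the exclusion also covers patients who, "in the opinion of the investigator (or qualified designee), present a risk of suicide".

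**4. The PBA-s exclusion.** Section 4.7.3 describes 11 items, each with severity 0–4 and frequency 0–4, and calls their product the PBA score. Without a named item, any of the 11 could exclude. Without a named rating, the product reaches 3 at severity 1 or 2: 1 × 3 = 3, 1 × 4 = 4, 2 × 2 = 4, 2 × 3 = 6, 2 × 4 = 8. Section 7.7.1 gives 3 and 4 as the only qualifying values, which fits a single 0–4 rating and not a product that can reach 16.

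**The case against.** The best defence is that the intent is plain. The Protocol elsewhere uses 'and' to list qualifying values: "If the patient has a positive score 1 and 2 on the suicidal ideation item or depressed mood item of the PBA-s" concerns a single rating, which cannot be 1 and 2 at once. Read the same way, questions 3, 4, and 5 means any of them, and Section 7.7.1 treats the list as equivalent to a score of at least 3. The PBA-s clause sits inside a bullet devoted to suicidality. All of this stands, and it is why the point is minor. It does not make the text safe to follow as written, because a site has to infer the meaning from another paragraph.

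Several stronger readings are tempting, and the documents do not support them:

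- **That the referral rule gives no C-SSRS score.** The lower tier in the same section applies one score to both scales, so 'score 3 and above' most naturally covers both as well. The inserted parenthesis makes this harder to see.
- **That the referral rule is uniquely narrow.** The exclusion and stopping rules carry the same list.
- **That most qualifying patients would be missed.** Nothing in the documents gives the distribution of answers.
- **That the PBA-s backstop is usually absent.** In Section 1.3 the abbreviated PBA-s is marked at 6 of the 8 recurring contacts from week 13 to week 104 (not RV3 or RV5), and Section 4.6.4 extends the safety calls that include it to unscheduled visits.
- **That patients who stay in the study off drug have no referral route.** Section 4.7.3 provides for close monitoring and for referral at the investigator's judgment.

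**Conclusion.** Wrong as written, and minor. In four places the C-SSRS explanation, taken literally, conflicts with the cut of 3 that the Protocol otherwise uses consistently. The patients exposed are those with a yes to question 3 or 4 but not to all of 3, 4 and 5, and only where no other trigger applies. Their number cannot be estimated from the documents. The PBA-s exclusion is a separate drafting gap that could exclude patients for reasons other than suicidality.

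The claim that the list is narrower rests on the assumption of five yes/no questions and holds under both scorings tried. No statistical result depends on it. SAP 2.1 states that the SAP follows Amendment 04 and that Amendment 05 was not implemented. The wording in force under Amendment 04 is not shown, so the effect on conduct is unknown.

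**What to change.** - **Section 4.7.3, referral rule:** print *C-SSRS suicidal ideation score ≥3*, so that the score is attached to the C-SSRS.
- **Synopsis 1.1 and Sections 4.5, 4.7.3 and 7.7.1:** change the explanation to a yes to *any of questions 3, 4 or 5*, once the sponsor confirms that the score is the highest-numbered question answered yes. If it is scored another way, delete the explanation and keep only the score.
- **Synopsis 1.1 and Section 4.5, PBA-s clause:** change to *PBA-s suicidal ideation item score ≥3 (i.e. 3, 4)*, with the sponsor confirming that this is the 0–4 severity rating.

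The lower tier in Section 4.7.3 and footnote 17 to Section 1.3 need no change. The cost is text edits in four places and two sponsor confirmations, with no change to assessments, visits or analyses.
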